Symptomatic, radiographic osteoarthritis (OA) affects over 27 million people in the United States; of this number, a significant proportion are affected by OA in the hip.²² Additionally, it is well known that older patients presenting with symptomatic labral tears are more likely to have OA. In fact, it is estimated that 25% of the general adult population has some type of cartilage defect.² Despite its prevalence the influence of preoperative arthritic changes on surgical outcomes is controversial. A recent systematic review gave a grade Cc recommendation for hip arthroscopy for the treatment of mild to moderate hip arthritis (conflicting).¹⁴ Another systematic review concluded that although some benefit is achieved in arthritic patients, the presence of cartilage defects at the time of surgery results in poorer outcomes than cases with normal cartilage.²³ There is an abundance of discussion in the literature with a specific focus on the influence of pre-existing arthritis on hip arthroscopy outcomes.²⁴⁻³³ In order to highlight this influence, one group created a Kaplan-Meier survival analysis that showed a high rate of conversion to total hip replacement in patients aged over 50 years old, and within this cohort, patients with less than 2 mm of joint space (radiographic OA) were found to have an increased failure rate.³²

The distinction between radiographic arthritis and arthroscopically (directly visualized) identified arthritis is important. Several radiologic-surgical correlation studies³⁴⁻³⁶ in the knee have shown that direct visualization of joint tissues by arthroscopy is more accurate in diagnosing cartilage loss and meniscal damage, making an arthroscopic exam the gold standard of investigation before definitive treatment planning in the knee.³⁶ This standard has not yet been achieved in the hip.

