Very little formal investigation has been performed to study the influence of age on hip arthroscopy outcomes; as such, there is currently no consensus on age as a predictor of outcome. Khanduja and Villar¹² recommend arthroscopy to be reserved for patients aged less than 50 years old. Philippon et al.³² reported outcomes after FAI in patients aged 50 years or older at a minimum 1-year follow-up and found that patients primarily achieved surgical success, though with a 20% conversion to total hip replacement (with a higher incidence in patients with > 2 mm of joint space). Larson et al.²⁴ also showed a failure rate that was dependent on age; however, a formal comparison was not made. Byrd and Jones³⁹ showed worse outcomes in older men. Although there have been studies looking at age secondarily in patients with labral tears, there is no prospective evidence to endorse or refute a recommendation of hip arthroscopy for patients of any age being treated for a tear of the acetabular labrum.

Preliminary Data

Our group recently performed a large retrospective case-control series looking at the influence of pre-operative arthritis and age as predictors of long-term outcomes following arthroscopic labral repair.⁴⁰ Over the course of the study period, which spanned 8 years and 200 patients, our management evolved to reflect the current practice of abstaining from arthroscopy in patients with less than 2 mm of joint space on plain standing radiographs. In spite of this, we continue to routinely encounter cartilage defects intra-operatively. Such findings can be explained by evidence stating conventional radiographic measures are poor predictors of actual arthritis in the hip.⁴⁸ Although it is possible that focal cartilage defects seen at arthroscopy are incidental findings.⁴²

Most studies attempt to eliminate radiographically evident severe arthritis by excluding patients who demonstrate less than 2 mm of joint space on standing antero-posterior hip radiographs at the time of surgery. However, based on our results, we suggest that the presence of Outerbridge grade 4 arthritic changes noted at the time of arthroscopy can be used adjunctively to identify patients who will fare poorly after hip arthroscopy for labral pathology. Interestingly, despite the apparent influence of arthroscopically identified arthritis portending worse outcomes (Odds ratio=2.5), our preliminary results suggest age is a stronger predictor (Odds ratio = 7) of diminished surgical outcomes.

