Determining which patients, using age and arthritic burden as predictors, can benefit from labral repair is paramount for several reasons. Showing arthroscopic repair is of little or no benefit to a specific cohort can reduce the number of unnecessary surgeries performed, increase the use of conservative therapy (if validated) and reduce the interval between diagnosis and total hip replacement. Additionally, proving a benefit exists from arthroscopic repair in a certain subset of the population will substantiate the need for developing a treatment algorithm in older patients presenting with labral tears and some degree of pre-existing arthritis. Furthermore, conservative physical therapy may prove to be of equal or greater benefit than arthroscopic repair in select patients. If true, this study will be a landmark for providing the evidence needed to recommend conservative treatment as an efficacious alternative in addition to providing a foundation for future research on this topic.

II. SPECIFIC AIMS:

Specific Aim 1: To evaluate if physical therapy alone or arthroscopic labral repair and physical therapy is of greater benefit to patients presenting at age 40 with tears of the acetabular labrum.

Hypothesis 1.1: Physical therapy will result in a significant difference in mHHS scoring at 12 months when compared to baseline.

Hypothesis 1.2: Arthroscopic labral repair will result in a significant difference in mHHS scoring at 12 months when compared to baseline.

Hypothesis 1.3: Arthroscopic labral repair and physical therapy will be superior to physical therapy alone in improving function and alleviating symptoms at 12 months when compared to baseline, as judged by the mHHS.

Hypothesis 1.4: Hypotheses 1.1-1.3 will hold true at 24 months and beyond.

Hypothesis 1.5: Functional outcome scores collected at the completion of PT will not significantly differ from those collected at 12 and 24 months and beyond in the same group.

Specific Aim 2: To evaluate the effect of arthritic burden on short term outcomes following arthroscopic labral repair.

Hypothesis 2.1: In the surgical treatment group, subjects with arthroscopically proven severe osteoarthritis (Outerbridge grade 4) will do more poorly on validated outcome measures, specifically the mHHS, after arthroscopy than subjects with less severe osteoarthritis (Outerbridge grade ≤ 3).

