We plan to track the effects of OA on outcomes through identification and localization of OA at the time of arthroscopy using a mapping technique (see diagram). After complete visualization of the intra-articular space, as is standard practice in hip arthroscopy, classification of any existing osteoarthritis will be done according to the Outerbridge grading scale. Using this system, we are able to categorically group subjects based on location and severity of disease. If multiple lesions are present, subjects will be characterized by the most severe grade. Furthermore, based on the data gathered through meeting hypotheses 1.1-1.4, we will subdivide primary outcome scores into four categories.⁶⁰ Category I, excellent outcomes (mHHS ≥ 90); Category II, good outcomes (mHHS ≥ 80); Category III, fair outcomes (mHHS ≥ 70), and Category IV, poor outcomes (mHHS < 70). The likelihood of outcomes based on Outerbridge grading and outcome category will be determined through odds ratios. Analysis will be carried out using Chi-squared tests. Significance is set at $P < 0.05$. Linear regression analysis will be performed to detect if any relationship exists between the severity of osteoarthritis and short-term outcome scoring.

Hypothesis 3.1:

This is an exploratory hypothesis whose assessment will no influence the other data sets. Prior work by other groups has demonstrated that evaluation of arthritic burden by conventional measures (Kellgren-Lawrence and Tonnis grading) are not indicative of the severity of arthritis found at the time of arthroscopy.⁵⁸ We will explore this phenomenon in our own cohort of subjects, specifically those in the surgical group and report our findings. We will correlate our findings for significance.

Power Analysis:

Specific Aim 1, Hypotheses 1.1-1.4: *To evaluate if physical therapy alone or arthroscopic labral repair and physical therapy is of greater benefit to patients presenting at age 40 with tears of the acetabular labrum.*

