Hypothesis 2.1 was powered on the basis of our prior work where 33% of study participants had grade 4 Outerbridge changes the time of arthroscopy. Dividing our cohort into two subgroups: 1) Those with grade 4 changes and 2) Those without. We will need 12 subjects with grade 4 changes in order to perform adequate sub-group analysis.⁶³ Powered to 80% and 5% significance level. Hypothesis 2.2 is another sub-group analysis that will be conducted in a similar fashion to that of hypothesis 2.1. However, the two groups will be categorized into: 1) cartilage defects at or near the chondro-labral junction and 2) cartilage defects not at or near the chondro-labral junction. We cannot control the heterogeneity of the subjects enrolled, but based on this analysis we expect to meet our target enrollment. Hypothesis 2.3 will be analyzed via linear regression and is appropriately powered.

Specific Aim 3 is exploratory. Since we are recruiting subjects for the main purposes of determining outcomes, we recognize that we may be underpowered for the definitive analyses of our radiographic correlation hypotheses. Nevertheless, we anticipate that we will enroll sufficient numbers of subjects to draw an association or at the very least, trend patient outcomes with degree of joint space narrowing, Kellgren-Lawrence grading, and Tonnis grading. There should also be sufficient numbers to preliminarily assess any correlations between pre-operative Kellgren-Lawrence and Tonnis grades with the Outerbridge classification at the time of arthroscopy.

VI. RISKS & DISCOMFORTS

Conservative Treatment: Subjects can expect the routine discomfort associated with any therapeutic procedure. Complications may include muscle soreness, pain, and increased edema or muscle fatigue.

Operative treatment: Since surgery is not considered a research procedure (only the randomization into the surgery group is considered a research procedure, as explained above) surgical risks are explained in the surgical consent process.

In the rehabilitation period, patients will be subject to the same potentials discomforts as those subjects in the conservative treatment group as the physical therapy protocols for both groups are identical. In both treatment groups every effort will be made to minimize the risk of adverse events and patient discomfort.

VII. POTENTIAL BENEFITS:

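### The Aim 2 analyses carry no age term, so the comparisons for Hypotheses 2.1 and 2.3 can credit part of an age effect to arthritis

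*Combined protocol and SAP*

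**What the plan says.** Specific Aim 2 reads: "To evaluate the effect of arthritic burden on short term outcomes following arthroscopic labral repair". Under it, Hypothesis 2.1 compares Outerbridge grade 4 with lower grades in the surgical group. Hypothesis 2.2 concerns cartilage defects at or near the chondrolabral junction. Hypothesis 2.3 compares subjects with and without joint space narrowing at 6 and 12 months.

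Section V (Hypothesis 2.1, 2.2, and 2.3) gives the methods. mHHS is cut into four categories, and "The likelihood of outcomes based on Outerbridge grading and outcome category will be determined through odds ratios". Then: "Analysis will be carried out using Chi-squared tests". Finally: "Linear regression analysis will be performed to detect if any relationship exists between the severity of osteoarthritis and short-term outcome scoring". The Power Analysis adds two-subgroup comparisons for 2.1 and 2.2, and for the third hypothesis says: "Hypothesis 2.3 will be analyzed via linear regression and is appropriately powered". Neither place names a covariate, an age stratum or a multivariable model.

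Section I says of age and arthritis that "older patients presenting with symptomatic labral tears are more likely to have OA" (Arthritis), and that "our preliminary results suggest age is a stronger predictor (Odds ratio = 7) of diminished surgical outcomes", against an odds ratio of 2.5 for arthritis found at arthroscopy (Preliminary Data). The Implications paragraph names age and arthritic burden together as the predictors of interest.

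**The concern.** Outerbridge grade and joint space narrowing are characteristics that subjects bring with them. Randomisation balances age between treatment arms, but not between arthritis grades within an arm. The plan's own background supplies both links of a confounding path: age goes with OA, and age goes with poor outcome. An unstratified chi-squared test cannot separate the two, and a regression on OA severity alone does not.

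At stake is how the result is used. The protocol hopes to identify a cohort for whom repair brings little benefit, and it already suggests grade 4 change as a marker of patients who do badly. If part of the difference is due to age, that cohort could be defined by the wrong characteristic, or the weight given to arthritis could be too large.

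**Working it through.** **The plan's own figure.** The only number given for Hypothesis 2.1 is 12 grade 4 subjects. It matches the stated 33% prevalence applied to 35 surgical completers: 0.33 × 35 = 11.55, rounded up to 12. The 80% power attached to it cannot be reproduced, because Aim 2 is given no effect size or SD. The point here disputes no printed number.

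**Inputs to the illustration.**
- From the documents: age odds ratio 7 (Section I, Preliminary Data).
- Assumed: no true grade 4 effect; risk of poor outcome in younger subjects (p0) of 15% to 40%; share of older subjects 40% v 70%, 30% v 70% or 30% v 80% (lower grades v grade 4); alternative age odds ratios of 2 and 3, in case the 7 does not carry over to subjects aged 40 and older.

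**Formulas.**
- Risk in older subjects: p1 = OR × p0/(1 − p0) ÷ [1 + OR × p0/(1 − p0)].
- Risk in a grade group with older share s: q = s × p1 + (1 − s) × p0.
- Crude grade 4 odds ratio: [q4/(1 − q4)] ÷ [qL/(1 − qL)], where qL is the risk in the lower-grade group.

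**One case in full.** p0 = 0.25, age odds ratio 7, shares 40% v 70%.
- p1 = 2.333/3.333 = 0.70.
- q4 = 0.7 × 0.70 + 0.3 × 0.25 = 0.565.
- qL = 0.4 × 0.70 + 0.6 × 0.25 = 0.430.
- Crude odds ratio = (0.565/0.435) ÷ (0.430/0.570) = 1.299/0.754 = 1.72.

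With age odds ratio 2, p1 = 0.40, q4 = 0.355, qL = 0.310, and the crude odds ratio is 0.550/0.449 = 1.23.

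**Full range, p0 from 15% to 40%.**

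| Older share, lower v grade 4 | Age OR 2 | Age OR 3 | Age OR 7 |
|---|---|---|---|
| 40% v 70% | 1.22-1.23 | 1.36-1.38 | 1.68-1.74 |
| 30% v 70% | 1.31-1.32 | 1.53-1.54 | 2.05-2.07 |
| 30% v 80% | 1.40-1.41 | 1.68-1.72 | 2.41-2.54 |

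Every entry should be 1.0 if the comparison isolated grade 4.

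**Cost of adjusting.** Adding age multiplies the variance of the OA coefficient by 1/(1 − r²), where r is the age-OA correlation (not given in the documents). At r = 0.3 this is 1/0.91 = 1.10; at r = 0.5 it is 1/0.75 = 1.33. To keep the same precision, 12 grade 4 subjects would become about 13 (12 × 1.10 = 13.2) or 16 (12 × 1.33).

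**The case against.** The strongest reply has five parts.

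- **The odds ratio of 7 may not transfer.** It comes from a retrospective series whose age range and cut-point are not stated, and this trial enrols only from age 40. Restriction removes some age variation; if the cut-point lay near 40, much of the contrast would be gone. Nor do the documents say whether the 7 and the 2.5 were mutually adjusted. This stands, and is why the table includes age odds ratios of 2 and 3.
- **The age link is stated for OA in general.** A reader might infer that age varies widely here and rises with Outerbridge grade. No text documents either. The absence of an upper age limit does not establish the enrolled spread. The same Background separates radiographic from arthroscopic arthritis and allows that focal defects may be incidental. The rationale for the age criterion, that OA missed by imaging is likelier from 40 on, makes the link plausible, but for grade 4 it remains an inference.
- **Hypothesis 2.2 is different.** Nothing ties age to defect location, and 2.2 is worded as prognosis. Extending the point to it at full strength is not supported.
- **Much of the wording is associational.** A crude association can answer a prognostic question, so it goes too far to say that Aim 2 would be left unanswered. But the aim itself speaks of an effect, and a crude estimate does not support that word.
- **The regression text is silent on covariates; it does not exclude them.** That fits under-specification better than a decision to ignore age. The chi-squared analysis, however, is unadjusted as written, and silence leaves the choice of model until after the data are seen.

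**Conclusion.** The point holds for Hypotheses 2.1 and 2.3. As written, their analyses can assign part of an age effect to arthritis, and on the plan's own statements the likely direction is overstatement.

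The size is not fixed by the documents. Under the assumed age splits and no true grade 4 effect, the spurious crude odds ratio runs from about 1.2 (age odds ratio 2, mildest split) to about 2.5 (the full 7, most extreme split). A reader might infer from the upper end that age alone explains the preliminary arthritis odds ratio of 2.5. The documents do not support that: it needs the full 7 to carry over, the widest split shown and no grade 4 effect at all, and none of these is established. The randomised comparison in Aim 1 is not affected.

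**What to change.** In Section V, for Hypotheses 2.1 and 2.3:

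1. Pre-specify linear regression of continuous mHHS on the OA term with age as a continuous covariate.
2. Fit it at each hypothesis's stated time points: 6 and 12 months for 2.3. Hypothesis 2.1 states no month, so Section V should name one.
3. For 2.3, which unlike 2.1 is not limited to the surgical group, add a treatment-arm term if both arms are included.
4. Base any statement about the effect of arthritis on the age-adjusted estimate. Report the crude odds ratios beside it, labelled as unadjusted associations.

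For Hypothesis 2.2, give an age-adjusted estimate as a supporting analysis only.

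The change is to wording. Age is an eligibility item, so it is known for every subject, and linear regression is already planned. The price is one degree of freedom and the variance inflation shown above (1.10 to 1.33 for r of 0.3 to 0.5). With only about 12 grade 4 subjects expected, that loss of precision is noticeable and should be acknowledged in the plan.

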Hypothesis 2.2: Cartilage defects at or near the chondrolabral junction are prognostic indicators of worse outcomes as determined by the mHHS.

Hypothesis 2.3: Subjects with any degree of joint space narrowing (classified by Tonnis and Kellgren-Lawrence grading, see below) on plain radiographs will have more pain, regain less function, and do more poorly based on validated outcome measures, specifically the mHHS, at 6 and 12 months than subjects without any degree of joint space narrowing on plain radiographs.

EXPLORATORY Specific Aim 3: To evaluate the relationship between joint space narrowing on plain radiography and arthroscopically proven osteoarthritis.

Hypothesis 3.1: Tonnis grading and Kellgren-Lawrence grading on plain radiography are not predictive of the severity of arthritis at the time of arthroscopy.

Specific Aim 4: To analyze the data of subjects crossing over from PT alone to PT and surgery.

Hypothesis 4.1: Primary outcome scoring (mHHS) at 12 and 24 months after cross to surgery and PT will differ significantly from those initially randomized to surgical treatment.

Hypothesis 4.2: Baseline scores on outcome measures of those subjects crossing over will not differ significantly from those obtained at the time of crossover.

III. SUBJECT SELECTION & ENROLLMENT:

Study Overview: This is a prospective randomized control trial (RCT), which will enroll subjects with a clinically diagnosed tear of the acetabular labrum. Subjects who have been diagnosed with a labral tear in clinic will receive conservative physical therapy treatment alone or arthroscopic surgical labral repair and physical therapy. If it is discovered that there is unexpected pathology at the time of arthroscopy for subjects in the surgery group, those subjects will be removed from the study. This is due to the possibility that the source of pain is less likely a result of the dysfunction of the labrum and more likely due to aberrant extra-articular biology. We will use validated outcomes measures that include the mHHS, LEFS, HOS, NAHS, and iHOT-33 (see below) and review the medical record for physical exam findings to track patient progress throughout their involvement in the study which will continue for as long as they are a patient of the PI. Study procedures will be complete when the last enrolled subject completes 24-month follow-up and completes the corresponding surveys.

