Our Primary Outcome is change in the modified Harris Hip Score at 12 months and 24 months. Secondary outcomes include changes in other validated outcomes measures patient satisfaction, and degree of improvement on physical exam. The influence of OA severity (Outerbridge scoring) and location of OA will also be analyzed to determine if they have an effect on the aforementioned outcome measures. Satisfaction will be assessed by an exit questionnaire (See section IV). In addition to gauging satisfaction, this questionnaire will ask subjects how they felt about their participation in the study. (See section IV)

Inclusion and Exclusion Criteria:

Inclusion criteria	Rationale
Age 40 or greater	Higher likelihood of undetectable OA on imaging
Orthopedic surgeon determines symptoms are consistent with a labral tear.	Required for treatment
Availability of hip radiographs and MRI	Needed to assess eligibility and comparison for specific aim 3
Willingness to undergo randomization and ability to understand and sign informed consent document	Ability to understand study and consent willingly

Exclusion criteria	Rationale
Unexpected pathology at the time of arthroscopy	Source of pain less likely to due dysfunction of the labrum and more likely due to aberrant extra-articular biology
Same site surgery	Complex anatomy
Contraindication to surgery or physical therapy	Cannot tolerate either treatment grouping
Alternate form of PT for greater than 6 weeks	Will negatively augment results. May affect recruitment.

Selection and enrollment:

We will enroll 122 consecutive subjects meeting the aforementioned criteria. Subjects will be randomized into conservative or surgical treatment arms. All potential subjects on the clinic schedule of the investigator will be pre-screened for eligibility based on age, clinical assessment, and previous medical history.

All eligible subjects will be approached at an outpatient clinic visit. Those who initially meet inclusion criteria will be introduced to the study and given a research consent form that they have the opportunity to take home and to review.

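### Aim 2 bands follow-up mHHS by absolute level across non-randomised arthritis groups, with no baseline term, although the plan defines its primary outcome as change

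*Combined protocol and SAP*

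**What the plan says.** The Study Overview in section III sets the outcome: "Our Primary Outcome is change in the modified Harris Hip Score at 12 months and 24 months". It then says that the severity and location of osteoarthritis "will also be analyzed to determine if they have an effect on the aforementioned outcome measures". For the mHHS, that points to change.

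The Aim 2 hypotheses are mixed. Hypothesis 2.1 says that Outerbridge grade 4 hips "will do more poorly on validated outcome measures, specifically the mHHS, after arthroscopy than subjects with less severe osteoarthritis", which can be read as final status. Hypothesis 2.2 is worded as prognosis. Hypothesis 2.3 says that subjects with joint-space narrowing "will have more pain, regain less function, and do more poorly based on validated outcome measures, specifically the mHHS, at 6 and 12 months", and regaining function is a statement about change.

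The analysis text in section V (Hypothesis 2.1, 2.2, and 2.3) says "we will subdivide primary outcome scores into four categories". Excellent is 90 or more and good is 80 or more; the rest are "Category III, fair outcomes (mHHS ≥ 70), and Category IV, poor outcomes (mHHS < 70"). Bands are related to Outerbridge grade by odds ratios and chi-squared tests at P < 0.05. A regression follows: "Linear regression analysis will be performed to detect if any relationship exists between the severity of osteoarthritis and short-term outcome scoring". The Power Analysis assigns Hypothesis 2.3 to linear regression. Nowhere in the Aim 2 text of section V does baseline mHHS appear, either as part of the outcome or as a covariate.

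**The concern.** The cut-offs at 90, 80 and 70 make sense only for an attained score, so the banded analysis is explicitly one of level. The regression does not say whether it uses level or change. Neither is tied to the change outcome in the Study Overview.

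This matters more in Aim 2 than in Aim 1. Randomisation balances baseline mHHS between the Aim 1 arms in expectation, so leaving baseline out there mainly costs precision. Outerbridge grade, lesion location and joint-space narrowing are not assigned at random, and any baseline difference between those groups passes in full into a comparison of follow-up levels. A hip that goes from 50 to 75 gains 25 points and is rated fair; one that goes from 72 to 90 gains 18 and is rated excellent.

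The Implications part of section I says that the results are meant to show which patients, by age and arthritic burden, benefit from repair. That is a question about response. A difference already present before surgery should not be able to pass for a difference in response.

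**Working it through.** **Inputs from the documents.** 35 completers per arm, a 10-point difference, 80% power and a one-sided 5% t-test (Power Analysis, Aim 1). 33% of hips with grade 4 changes and 12 grade 4 subjects needed (Power Analysis, Aim 2).

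**The plan's own figure.** 0.33 × 35 = 11.55, which rounds up to 12. So 12 matches the expected number of grade 4 hips among 35 surgical completers. It cannot be reproduced as an 80%-power figure, because no effect size or SD is given for Hypothesis 2.1. The illustration uses 12 grade 4 and 35 − 12 = 23 other hips.

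**SD (assumption).** The documents give none. Solving the Aim 1 calculation for SD with the normal approximation: SD = 10 × √(35/2) / (1.645 + 0.842) = 41.83 / 2.487 ≈ 16.8. The exact t calculation gives 16.66, used below as about 16.7.

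**Level analysis, equal true gain.** If both groups gain the same amount, the expected difference in follow-up level equals the baseline gap, and the expected difference in change is zero.

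Standard error of the difference = 16.66 × √(1/12 + 1/23) = 5.93, with 33 degrees of freedom and a two-sided critical value of 2.03.

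- Gap 5: noncentrality 5 / 5.93 = 0.84; significant in 13% of trials two-sided (21% one-sided).
- Gap 10: noncentrality 10 / 5.93 = 1.69; significant in 37% two-sided (50% one-sided).

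A regression of level on grade 4 yes/no is the same test. An analysis of change keeps its nominal 5% rate in this scenario.

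**Four-band chi-squared test.** This is the test named for the bands. It was simulated with 12 v 23 hips, normal scores with the same SD, and an assumed mean follow-up score in the comparison group:

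| Comparison mean | Gap 0 | Gap 5 | Gap 10 |
|---|---|---|---|
| 75 | 5% | 6% | 14% |
| 80 | 5% | 8% | 18% |
| 85 | 5% | 9% | 21% |

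**Odds ratio for a poor result.** Take a comparison mean of 80 and a 10-point gap, so that the grade 4 mean is 70. The share below 70 is then 50% in grade 4 and about 28% in the others (SD 16.8). The odds ratio is (0.50/0.50) / (0.276/0.724) ≈ 2.6, with no difference in gain.

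**Ceiling.** With baseline mean 60, gain 20 and scores capped at 100.1, a 10-point gap gives a level difference of −9.3 and still about 37% significant. The cap barely matters here.

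**Baseline-adjusted level.** With equal SDs at baseline and follow-up, the adjusted difference is gap × (1 − r), where r is the baseline to follow-up correlation. For a 10-point gap this leaves 7, 5 or 3 points at r = 0.3, 0.5 or 0.7. Adjustment removes part of the gap, not all of it.

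**The case against.** Four objections carry weight.

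First, the regression sentence does not say that level is used. Read with the Study Overview, it could mean change. A reader might infer that the whole of Aim 2 is committed to level; the documents support that only for the bands. For the regression, which is the analysis assigned to Hypothesis 2.3, the defect is that the outcome and covariates are unspecified.

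Second, final status is a legitimate target for a prognostic question, and Hypotheses 2.1 and 2.2 are worded largely that way. If the aim is to say where a grade 4 hip ends up, baseline is part of the prognosis and a level analysis is not biased. This stands. But the plan does not say that this is its target, and its outcome definition and Hypothesis 2.3 point to change.

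Third, a reader might infer that arthritic hips do start lower, so that the result will be distorted. The documents give no baseline mHHS by Outerbridge or radiographic grade, and the Preliminary Data allow that focal defects may be incidental. With no baseline gap there is no distortion.

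Fourth, the 13% and 37% belong to a t-test or a binary-grade regression on level. The test named for the bands gives smaller figures.

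A reader might also infer that the trial is looking for a reason to withhold surgery from arthritic patients. The Implications text does not support that: it equally foresees demonstrating a benefit in a subset with pre-existing arthritis.

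**Conclusion.** The point holds as a mismatch between the Aim 2 analysis and the plan's own outcome definition, with a risk of bias that depends on an unknown baseline gap. The bands are explicitly level-based, the regression leaves level or change open, no baseline term is named, and the groups compared are not randomised.

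If arthritic hips start lower, a level analysis can present that gap as poorer response to repair. For a 5- or 10-point gap with equal gains, a significant difference would appear in about 13% or 37% of trials by two-sided t-test or binary-grade regression on level, and in about 6-9% or 14-21% by the four-band chi-squared test, against a nominal 5%. These figures are illustrations. They rest on 12 v 23 hips, an SD of about 16.7 back-solved from Aim 1, and assumed comparison means of 75 to 85. No size was worked out for Hypotheses 2.2 and 2.3.

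This concerns a secondary aim and should be corrected before analysis. It does not touch the randomised comparison.

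**What to change.** For Hypotheses 2.1 to 2.3:

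- Name change in mHHS from baseline as the main outcome, matching the Study Overview, and report the mean difference in change between arthritis groups with a 95% CI.
- Report baseline mHHS by arthritis group, so that any starting gap is visible.
- As a supporting analysis, regress follow-up mHHS on arthritis group with baseline mHHS as a covariate. State that this answers a different question and can disagree with change when groups differ at baseline.
- Keep the four bands as a description of final status, and say that they are not evidence of response to surgery.

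The cost is analysis-plan wording only, since baseline mHHS is already needed for the paired tests in Aim 1. The downside is that change is limited by the scale ceiling in subjects who start high.
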